6. STUDY PARAMETERS/ENDPOINTS

6.1. Main study parameter/endpoint

Co-primary study endpoints:

1. Days alive out of hospital (superiority endpoint), within 14 days after study enrolment
2. Days on Therapy (DOT) with antibiotics (superiority endpoint), within 14 days after study enrolment
3. Adverse outcome (non-inferiority safety endpoint)
 - For initially non-admitted patients: any admission or death within 30 days after study enrolment
 - For initially hospitalised patients: i) any readmission, ii) ICU admission \geq 24 hours after hospitalisation, or iii) death within 30 days after study enrolment

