10.2. Randomisation and blinding

Due to the nature of the intervention, blinding is not possible. After all eligibility criteria have been verified and informed consent has been obtained, randomisation will be performed using the built-in randomisation module of the eCRF system. Allocation will be concealed until the moment of randomisation. To this end, block randomisation will be used with variable blocks of size 2, 4 and 6. Randomisation will be stratified by centre. After the decision to randomise the patient is made, patients will not be excluded from the trial. If the allocated intervention is not applied for any reason, this will be recorded and follow-up for the participant will be completed.

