10.3. Data collection

A secured electronic case record form (eCRF) will be specifically designed for this study for data capture.

- **Main study** (Follow up until 30 days) – Standard of care clinical and microbiological data will be collected but not study specific biological samples will be obtained for research purposes. The **clinical data set** will summarize the illness episode and outcome, microbiological testing and antimicrobial use including the total hospitalisation or, in case of discharge, the time window defined on the primary endpoints. Information including data for health economic analysis will be collected on day of enrolment, day 14 (visit window: day 14 – 16) and on day 30 (visit window: day 30 – 32), after randomisation. Participants/LAR will be asked to consent to being contacted by study staff for the follow-up visits to minimise loss to follow-up. In case of failure to successfully contact participant/LAR at the end of trial participation, the participant's general practitioner/family doctor will be contacted to complete information on the primary endpoints.
- **Extension study** – in a subset of patients (around 300 patients per arm), patients that were initially hospitalised will be followed post-discharge at month 3 (visit window: +7 days) and month 6 (visit window: +7 days) to study health economic and social impact.
- Qualitative Evaluation: Only clinician (semi-structured) qualitative interviews

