SD	Relevant effect size	Alpha	Beta	Correction	Sample size per arm
3	1	0.025	0.1	1.15	257
4	1	0.025	0.1	1.15	457
5	1	0.025	0.1	1.15	714
6	1	0.025	0.1	1.15	1,028
7	1	0.025	0.1	1.15	1,399

For adverse outcome, if we assume an incidence of 10% the sample size would be 780 per arm, and if we assume 5% it would be 412, in both cases using a non-inferiority margin of 5% (Table 2). A high power for adverse outcome is considered important because both the superiority and the non-inferiority hypothesis need to be confirmed in order to declare the intervention a success so a total of 780 adults per study arm would be required to reach 95% power

Table 2: Sample sizes for adverse outcome using different assumptions.

Incidence *	Non-inferiority margin	Alpha**	Beta	Sample size per arm
0.05	0.05	0.05	0.05	412
0.10	0.05	0.05	0.05	780

* same for intervention and control arm; ** one-sided alpha

To account for potential drop-outs we will aim for a **total of 1600 adults** in the study. The sample size includes participants that are randomised and does not include enrolled but non-randomised patients.

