13.3. Primary study parameter(s)

Descriptive statistics will be produced and tabular summaries will be presented, stratified according to the allocated group (rapid syndromic testing vs. control). Categorical data will be summarized by the number and percentage of patients in each category. Appropriate summary statistics will be used for continuous variables depending on the distributional assumptions. These include measures of central tendency (mean or median) and dispersion (standard deviation or inter-quartile range).

‘Days on antibiotic treatment’ and ‘Days alive out of the hospital’ will be analysed using a linear regression analysis, including as covariates stratification by age groups and predefined risk factors. Upfront we may expect that the assumption of normally distributed residuals is violated, in which case we will determine the confidence interval by bootstrapping.

Adverse outcome will be analysed using Cox proportional hazards regression adjusted for age groups and predefined risk factors. Risk differences and 90% CI will be inferred by comparing the cumulative incidence of failure at day 30 from the Cox model and bootstrapping for the confidence interval. A 90% CI will be used to be compatible with a one-sided alpha of 0.05.

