14.3. Withdrawal of individual patients

Patients are free to withdraw consent at any time without providing a reason. Patients who wish to withdraw consent for the study will have anonymized data collected up to the point of that withdrawal of consent included in the analyses. The patient will not contribute further data to the study. Data up to the time of withdrawal will be included in the analyses unless the patient appeals to the 'right to be forgotten' according to the national GDPR regulations. The investigator can decide to withdraw a patient from the study for urgent medical reasons. Enrolled patients meeting one or more of the exclusion criteria *prior* to randomisation, will be withdrawn by the investigator. Patients withdrawn prior to randomisation will be replaced (i.e. they will not count towards the sample size). Patients withdrawn after randomisation will not be replaced.

The participants cannot be enrolled at the same time into any interventional clinical study unless it is a COVID-19 study that does not interfere with this study. Patients may be co-enrolled in another observational study if the local study coordinators have been informed and have given their approval, to ensure the other study would not interfere with the results of this study or compromise patient welfare.

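### Does the rule on investigator withdrawal for urgent medical reasons open the 30-day safety endpoint to loss related to prognosis?

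*Combined protocol and SAP*

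**What the plan says.** Section 14.3 deals mainly with withdrawal of consent: data up to that point are used and the patient contributes nothing further. It then adds: "The investigator can decide to withdraw a patient from the study for urgent medical reasons". No time limit and no data rule are attached to that sentence. The sentence after it, on patients found to meet exclusion criteria, is limited to the period before randomisation. The section also says: "Patients withdrawn after randomisation will not be replaced".

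Section 10.2 says: "After the decision to randomise the patient is made, patients will not be excluded from the trial". It continues: "If the allocated intervention is not applied for any reason, this will be recorded and follow-up for the participant will be completed".

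Section 10.3 gives a fallback when the participant cannot be reached at the end of participation: the "general practitioner/family doctor will be contacted to complete information on the primary endpoints".

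The safety endpoint in section 6.1 reads, for those sent home: "For initially non-admitted patients: any admission or death within 30 days after study enrolment". For those admitted at first it is readmission, later ICU admission or death within 30 days. Section 13.3 says: "Adverse outcome will be analysed using Cox proportional hazards regression adjusted for age groups and predefined risk factors". The primary analysis is by intention to treat (section 13.2), and that section leaves the SAP to be prepared later.

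**The concern.** An urgent medical problem predicts admission, ICU care and death, which are the components of the safety endpoint. Suppose an investigator, who knows the arm, withdraws such a patient after randomisation and outcome collection ends there. The Cox model would censor the patient and treat later risk as the same as that of comparable patients who stay. Adjustment for age group and predefined risk factors would not fully capture an acute deterioration.

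The trial can succeed only if non-inferiority is shown on this endpoint (section 13.1). Events hidden in the test arm would make a false non-inferiority claim more likely. Read literally, each neighbouring rule misses the case. The sentence on no further data concerns consent, the promise of completed follow-up concerns a test not applied, and the family-doctor route concerns failed contact.

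**Working it through.** **The plan's own figure.** Inputs from section 13.1: incidence 10% in both arms, margin 5 points, one-sided alpha 0.05, power 95%.

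n = (1.645 + 1.645)² × 2 × 0.10 × 0.90 / 0.05² = 779.2, so 780 per arm, as printed. The protocol says "To account for potential drop-outs we will aim for a" total of 1600. That is 800 per arm, an allowance of 20 per arm, or 2.5%.

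**Set-up.** The protocol gives no withdrawal rate, so every share below is an assumption. Take true risks at the margin (15% test, 10% control) and 800 per arm, that is 120 and 80 expected events. The chance of declaring non-inferiority is approximately

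P = Φ[(0.05 − (p₁ − p₀)) / SE − 1.645], with SE = √[p₁(1 − p₁)/800 + p₀(1 − p₀)/800].

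With nothing lost, P = 5.0%. This is an unadjusted approximation to the Cox-based risk difference.

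**Equal shares of would-be events lost.** If a share w is censored first, the observed risk is p(1 − w)/(1 − pw). For w = 5% this is 0.1436 (test) and 0.0955 (control). For w = 10% it is 0.1371 and 0.0909.

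| Events lost in | w = 5% | w = 10% |
|---|---|---|
| both arms | 6.3% | 8.0% |
| test arm only | 10.5% | 20.0% |
| control arm only | 2.7% | 1.4% |

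The first row rises only because equal shares mean unequal numbers: 6 test against 4 control patients, or 12 against 8.

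**Equal numbers of would-be events lost.**

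- 6 per arm: test 114/794 = 0.1436, control 74/794 = 0.0932, difference 0.0504, P = 4.8%.
- 12 per arm: test 108/788 = 0.1371, control 68/788 = 0.0863, difference 0.0508, P = 4.5%.

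**Withdrawn patients at raised but not certain risk.** With a proportion v of an arm withdrawn, an event risk r among them and their outcomes dropped, the observed risk is (p − vr)/(1 − v). Let r run from 30% to 80%.

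- 1% or 2% withdrawn in each arm: P = 4.7% or 4.4%.
- 2% test against 1% control: about 6% to 10%.
- 1% to 3% in the test arm and none in control: about 6% to 35%.

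So the error stays close to nominal when losses are balanced in number, and moves up or down only with imbalance.

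**What the text implies about collection.** Section 10.2 rules out exclusion once the decision to randomise is made. The only allocated procedure is a rapid test, awaited for at most 4 hours (section 8.2). Section 15.4 says no experimental treatment is involved. Follow-up consists of chart data, calls and questionnaires (sections 10.3 and 10.4). An urgent problem after randomisation would mainly prevent or overtake the test, and that is the case in which section 10.2 promises completed follow-up. The non-replacement sentence in section 14.3 is fully accounted for by withdrawals of consent, so it does not show that investigator withdrawals after randomisation are expected. Section 10.1 places rapid deterioration between arrival and randomisation and requires eligibility to be checked again then, which makes a pre-randomisation reading of the sentence plausible.

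**The case for a change.** The best case for a change is that the sentence speaks of withdrawal from the study, not from the test, and has no time limit, while the sentence after it does. A site could read it as ending data collection, and sites could differ. The trial is open-label, so decisions could differ by arm. As few as 6 or 12 test-arm patients, within the allowance of 20 per arm, would double or quadruple the error if all were would-be events and none were lost in control. Outcomes never collected may not be recoverable, intention to treat does not supply them, and clarifying would cost a sentence.

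Part of this stands. Section 14.3 has no data rule for this case, and its wording sits awkwardly beside section 10.2, so the two would read better if reconciled. The high figures are correct under their assumptions.

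The step from silence to loss does not stand. No section says collection stops, and the nearest rules point the other way. The largest figures need all losses in one arm. For patients sent home, an urgent problem that leads to admission is itself the endpoint event, so it need not hide a later one. There is also a partial second route. Deaths and in-patient hospitalisations are serious adverse events, documented in source whatever the cause (section 12.1). Those possibly related to the disease, procedure or device go to the sponsor through day 30 (section 12.2). That route does not cover unrelated events and does not name withdrawn patients.

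**Conclusion.** No change to the plan follows. The point is a missing detail, not a shown bias: section 14.3 is silent on data after an investigator withdrawal, and analysts and sites can fill the gap from section 10.2 and the intention-to-treat principle by continuing to collect 14-day and 30-day outcomes unless consent is withdrawn. How any outcomes still missing are handled, including whether unknowns are counted as failures, is one of several reasonable choices for the SAP.

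The harm is conditional on collection stopping, on such withdrawals occurring after randomisation, and on imbalance between arms. Their frequency is unknown and may be zero. With equal numbers of would-be events lost (6 or 12 per arm) the error is 4.8% or 4.5%. With one-sided loss of the same numbers from the test arm it would be 10.5% or 20.0%, and nothing in the protocol suggests that pattern. The sample size of 780 per arm and 1600 in total is unaffected. When a patient may be withdrawn on medical grounds is a clinical matter and is not judged here.

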15. ADMINISTRATIVE ASPECTS, MONITORING AND PUBLICATION

15.1. Steering Committee

The missions of the steering committee are to define the objectives of the research, to propose protocol modifications during the research, to organize the research, to determine the methodology, to coordinate information and to monitor the conduct of research. The steering committee will decide during ongoing research what to do in unexpected situation. The steering committee will meet regularly until the end of inclusions.

15.2. Handling and storage of data and documents

Data will be recorded in a secured electronic case record from (eCRF) specifically designed for this study and validated for authenticity, accuracy, reliability and consistent intended performance. An eCRF should be completed for each participant.

All information obtained during the study (except the ICF data) will be entered digitally in conformity with the applicable laws and regulations. All data (except the ICF data) will be coded using a unique study number. Data will be handled in accordance with local privacy regulations and the European General Data Protection Regulation (GDPR, 2016/679, effective as of May 25th, 2018)

15.3. Storage of samples.

A sample required for the CA-ARTI diagnostics will be taken in patients randomised to care with the addition of that diagnostic, according to local laboratory requirements.

15.4. Monitoring and Quality Assurance

Remote/centralized and/or on-site study monitoring will be carried out by the Sponsor. A monitoring plan will be scheduled and will define the monitoring frequency and procedures. Monitoring will start before recruitment begins, throughout the trial (data monitoring including but not limited to recruitment rates, consent procedures, access/storage of patient identifiers, sample handling for performing the diagnostic intervention test, data entry, data queries, unusual data patterns), between recruiting season and at the end of the trial (source document verification, collect trial supplies, close-out meetings/visits). We will use a risk adapted approach within the protocol design to enable safety reporting requirements to reflect the amount of safety data available and the level of risk for this non-interventional study. We refer to the monitoring plan for details.

This study does not involve any experimental treatment, but the diagnostic intervention may interfere with the standard of care and it involves data collection. The need for additional insurance for study patients may differ per country local regulations.

15.5. Public disclosure and publication policy

All information disclosed or provided by the Sponsor (or any company/institution acting on their behalf) or produced during the study, including, but not limited to, the protocol, the eCRF, and the results obtained during the course of the study, is confidential prior to the publication of results and in accordance to consortium agreement and open access regulations.

The detailed procedures for the review of publications are set out in the clinical trial agreement entered into with the Sponsor in connection with this study. These procedures are in place to ensure coordination of study data publication and adequate review of data for publication against the validated study database for accuracy. UMCU will adhere to all applicable local laws governing transparency in clinical trials including the trial posting on clinicaltrials.gov and all other applicable registrations.

